We currently spend great resources into avoiding substance abuse relapse and improving patient's compliance during the LT evaluation, but have omitted education regarding healthy lifestyle habits including physical activity and exercise, what might bring enormous benefits to LT worldwide. For patients with cirrhosis and ESLD, the period before liver transplantation is full of self-reflection and insight, education, and lifestyle changes. These behavioral tuning has allowed keeping the rate of alcohol recidivism at no more than 10% in most transplant centers, and a low prevalence for the use of tobacco products after LT. It is expected that any recommendation or prescription regarding physical activity would have greater acceptance and a more durable effect if properly administered once patients have reached ESLD, or while they are being evaluated for LT, as they become very receptive to make changes in their lifestyle as far as it helps to facilitate transplant candidacy. However, unlike diabetes mellitus and cardiac diseases, it is unknown for ESLD patients what the mode, intensity, and duration of exercise that will provide improved outcomes are. More importantly, there is a lack of knowledge regarding the safety of exercise with respect to hyperammonemia and occurrence of HE.

SPECIFIC AIMS

The primary aims of current study are to:

- Improve the physical fitness of patients with ESLD whom are potentially eligible for liver transplantation with a 12-week physical training program.
 - The hypothesis is that only patients enrolled in the active arm will improve their physical fitness, as determined by cardiorespiratory stress test and 6-minute walk test.
- Improve sarcopenia in patients with ESLD whom are potentially eligible for liver transplantation with a 12-week physical training program
 - The hypothesis is that only patients enrolled in the active arm will show an increase in the skeletal muscle area, as determined by CT-scan.

As secondary aims, this 12-week training program will look into:

- The changes in the ammonia and anaerobic/lactate thresholds at the end of the study for each group.
 - It is expected to find increased ammonia and anaerobic/lactate thresholds in the active arm, when compared to the control arm.
- The changes in anthropometrics (weight, BMI, waist circumference), and body composition at the end of the study for each group.

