Physical activity prescription will target \geq 10,000 steps/day, taking into account all activities performed throughout the day, although the increment in activity should be no less than 4000 steps/day above the baseline. Apart from walking, there will be no physical activity that would be favored in particular to all participants, but each one will be able to choose and perform the type of exercise of their preference. The $VO_{2\text{max}}$, ammonia, lactate and anaerobic thresholds observed on each subject will help better determine the intensity of exercise each patient should be able to tolerate safely.

Nutritional Intervention

Title: A physical activity program in end-stage liver disease
PI: [name]

Dietary advice will be provided at the beginning of the study and individually tailored to the participant's usual eating habits, with the following modifications:

- High in low glycemic-index foods and fiber
- Low in fat and cholesterol
- 500 kcal/d calorie restriction if obese
- A light snack at night.
- Protein amount at 1.2-1.5 g/kg/d
- Low sodium (<2000 mg/d) and water restriction to be defined as per standard of care.

Moreover, patients will receive a 10 g bid essential amino acid (EAA) supplement containing approximately 2.25 g/d of L-leucine and 5.2 g of branch-chained amino acids (Reginator, Prinova, Carol Stream, Illinois). This supplement should not affect the total daily caloric intake, or sodium restriction. The intention is to favor healthy food eating habits, along with enough protein to support muscle repair and building. Compliance to the dietary behavior changes will be assessed every 2 to 4 weeks by the LT nutritionist.

Behavioral Modification

The behavior modification theory will be applied in the form of a structured set of cues and questions between investigator and participant at each visit in order to provide individually tailored counseling to enhance internal motivation and facilitate behavior change toward physical activity and dietary improvement that are adaptable to each participant's usual habits.

Follow Up

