The study will occur over a total of 14 weeks, although duration of the intervention will consist of 12 weeks. The first two weeks will serve the purpose of identifying the baseline physical activity of each participant. During the second week all baseline studies/determinations will be completed, with randomization occurring by the end of week 2. Allocation will be stratified by presence or absence of refractory ascites.

Follow up visits for behavioral therapy will occur every 2 weeks for the first 8 weeks, and then on a 4-weekly basis (only active group). Nutritional consultation will occur every 2 to 4 weeks throughout the study (both active and control group). During each visit, the EAA supplement jar will be inspected for percent emptiness (in analogy to a pill count) in order to quantify adherence. Bi-weekly phone calls will be made to all subjects to enhance adherence to recommendations. Standard of care investigations (blood chemistries, hematology and coagulation, liver function tests, etc.) will be ordered according to the needs of the patient and the criteria of the investigator or responsible clinician. Clinical status and complications from portal hypertension, particularly variceal bleeding and HE, will be systematically investigated on each visit.

Research Tests - Variables to Measure

Prior to randomization each subject will be scheduled to undergo all baseline investigations, as follows (see Research Calendar below):

Cardiorespiratory stress test (CRET) and anaerobic threshold (Week -1, Day 1)

CRET will be performed early in the morning on a fasting state, following the maximal incremental cycle ergometry protocol from our Pulmonary Physiology Laboratory, and in agreement with the American Thoracic Society.(38) Briefly, test consists on having the patient on a cycle ergometer performing a progressively increasing work rate until reaching: volitional exhaustion, or termination by the medical monitor. The Borg Rating of Perceived Exertion Scale will be used to help titrate intensity of work rate (aiming for a level of 13 to 17). Gas exchange measurement for

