The 6MWT will be performed in agreement with the recommendations of the American Thoracic Society.(39) In brief, the test will be done indoors, along a long and flat enclosed corridor, aiming for as many laps (100 ft per half-lap) as possible, while patient is wearing a pulse oximeter. The investigator applying the test will use a stopwatch and write down heart rate and oxygenation, at baseline, and every minute until reaching a total of six minutes. The Modified Borg Scale will be used to rate shortness of breath and fatigue before and after the test. This test will be repeated after completion of the study period (12 weeks), and 6 months after LT.

Sarcopenia (abdomen CT-scan) (Week -1, Day 3)

A noncontrasted abdominal CT-scan will be used to measure the cross-sectional area of skeletal muscle at the level of the third lumbar vertebrae (L3). Images will be analyzed with SliceOmatic 4.3 (Tomovision, Montreal, Canada) measuring the cross-sectional area of skeletal muscle at this level (*i.e. psoas, paraspinals, quadratus lumborum, transversus abdominis, rectus abdominis, and internal and external obliques*). Muscle areas will be analyzed by an operator trained in musculoskeletal anatomy with tissue-specific Hounsfield unit thresholds (-29 to +150).(16) The L3 skeletal muscle area will be normalized to stature by the division of the muscle area by the height squared. Sarcopenia will be defined as a reduction in the L3 area of muscle mass $\leq 52.4 \text{ cm}^2/\text{m}^2$ in males and $\leq 38.5 \text{ cm}^2/\text{m}^2$ in females. This test will be repeated after completion of the study period (12 weeks), and 6 months after LT.

Nutritional consultation, anthropometrics, and body composition (Week -2, Day 3)

A dietitian or designated investigator will evaluate anthropometrics (weight, height, waist circumference), bioelectrical impedance, and whole-body dual energy X-ray absorptiometry scan (DXA). Bioelectrical impedance will be performed according to the manufacturer's recommendations: after overnight fasting, with subject in supine position with arms and legs abducted from the body, and source and sensor electrodes placed on the dorsum of both hand and foot on the right side of the body, respectively. After obtaining resistance (R), reactance (Xc)

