and phase angle (PhA), two analyses will be performed: PhA and bioelectrical impedance vector analysis (BIVA). PhA will be evaluated as a nutritional marker reflecting muscle mass. Sarcopenia will be defined as a PhA < 5.4°. Following normalization of R and Xc to patient's height (R/H, and Xc/H, respectively), R/H and Xc/H will be plotted as bivariate vectors on the R-Xc graph (expressed in Ohm/m) in order to obtain BIVA. Individual vectors for each patient will be calculated and analyzed to determine nutritional status, muscle mass, and hydration status. For DXA a standard protocol and quality assurance procedure will be followed. DXA will be used to estimate body composition. Briefly, before each DXA scan, the subjects' height, weight, gender, and race will be entered into the computer program. The subjects will be in a supine position on the DXA table with hands pronated and flat on the table. Total body mode will be selected for each scan, and scanning thickness will be determined by the DXA software. Anthropometrics, PhA, BIVA, and DXA will be repeated after completion of the study period (12 weeks), and 6 months after LT.

Blood Biomarkers

Myostatin and IGF-1 levels will be determined in blood (R&D Systems, Minneapolis, MN) at baseline and during week 12 visit to clinic. Also, at baseline and during week 12 visit blood EAA (high-performance liquid chromatography; vendor, City, State) will be quantified. The latter will be performed at [name] laboratory at no cost. [name] will be blinded to the source of serum samples. In order to facilitate blinding, blood samples will be processed by clinical coordinator into aliquots, de-identified, and stored at [name] laboratory for future assay running. Only the clinical coordinator and the PI will have access to the code that identifies the serum samples provided for EAA quantification.

Quality of life and metabolic profile (Week -2, Day 3)

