Unlike CRET, in the 6MWT each patient determines the intensity of their exercise according to symptoms and cardiorespiratory fitness. The 6MWT is thus considered a very safe procedure, and it has been performed (without electrocardiogram monitoring) in thousands of older persons and thousands of patients with heart failure or cardiomyopathy without serious adverse events. Although patients with cardiopulmonary disease may be at increased risk for arrhythmias or cardiovascular collapse during testing, it is very unlikely for a complication to be witnessed given the selection criteria followed during LT evaluation (as above).

The risks associated with placement of an IV catheter and blood collection from a vein are minor bleeding, bruising, infection (a small risk any time the skin is broken), or needing more than one attempt to locate veins.

Both CT and DXA scans are associated with exposure to small amounts of ionizing radiation. The abdominal CT-scan will be restricted to a simple phase (non-contrasted) in order to limit radiation exposure, and thus it should not exceed 10 mSv. Since the initial CT-scan is performed as part

Title: A physical activity program in end-stage liver disease
PI: [name]

of the LT evaluation (standard of care), the study will derive in radiation exposure of approximately 20 mSv. This is a very low radiation exposure that might be associated with a low additional increase in lifetime risk for cancer (1 in 1000 to 10,000). In the case of DXA, exposure per whole-body scan is similar to daily background natural radiation exposure (0.01 mSv).

The electrical current used in bioelectrical impedance is very small and thus unlikely to stimulate electrically excitable tissues, particularly cardiac and nervous tissues. Moreover, there are no reports of untoward effects among thousands of individuals in whom bioelectrical impedance analysis has been performed. Actually, the currents employed are very small and below the threshold of perception.

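### The protocol does not say that the person running the effort-dependent 6-minute walk test, a primary measure, is unaware of allocation or separate from the coach of the active arm

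*Combined protocol and SAP*

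**What the plan says.** - **Role of the test.** Under Specific Aims, the first primary hypothesis is judged "as determined by cardiorespiratory stress test and 6-minute walk test".
- **Effort.** Risks and Benefits notes that "in the 6MWT each patient determines the intensity of their exercise according to symptoms and cardiorespiratory fitness".
- **Tester.** The 6MWT section says: "The investigator applying the test will use a stopwatch and write down heart rate and oxygenation". It adds no condition on who this person is or what they know.
- **Timing.** Baseline tests are done before randomization (Research Tests). For the 6MWT, "This test will be repeated after completion of the study period (12 weeks), and 6 months after LT".
- **Coach.** Behavioral Modification describes a "structured set of cues and questions between investigator and participant at each visit", intended to raise motivation. Follow Up limits this to one arm: "Follow up visits for behavioral therapy will occur every 2 weeks for the first 8 weeks, and then on a 4-weekly basis (only active group". The note under the Study Calendar says the same.
- **CRET staff.** The CRET section describes a test "following the maximal incremental cycle ergometry protocol from our Pulmonary Physiology Laboratory", with a medical monitor who can end it. Risks and Benefits refers to personnel in charge of the test.
- **Masking elsewhere.** The person who quantifies amino acids "will be blinded to the source of serum samples" (Blood Biomarkers). CT scans go to an outside reader without identifiers (Data collection and handling). Step counts are hidden from controls (opening summary).

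**The concern.** The distance walked in six minutes depends on how hard the patient tries, and a tester can influence that. If the tester has spent 12 weeks motivating active-arm patients and has had no such contact with controls, encouragement at week 12 may differ between arms without anyone intending it. The stated hypothesis, that only the active arm will improve, is the kind of expectation an unblinded tester could bring to the test.

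Any such difference would enter the between-group comparison. The planned t-test or Mann-Whitney test (Statistical analysis) would count it as a training effect, and it could not readily be separated out after data collection. The same applies, with less at stake, to the post-transplant test, which serves a secondary aim. The CRET is also exposed in part, because it normally ends when the patient is exhausted.

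**Working it through.** **Reading the text**

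| Question | What the protocol gives |
|---|---|
| Is the 6MWT primary? | Yes, together with the CRET (Specific Aims) |
| Does it depend on effort? | Yes (Risks and Benefits) |
| Who runs it? | An investigator, not further described (6MWT section) |
| Who coaches? | An investigator, not further described (Behavioral Modification) |
| Which arm is coached? | Active only (Follow Up; Study Calendar note) |
| Is the tester blinded or separate from the coach? | Not stated anywhere |
| At which tests is allocation already fixed? | Week 12 and 6 months post-transplant, not baseline |

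The text therefore permits the coach to run the follow-up tests. It does not say that the coach will.

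**Illustration of size**

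The plan has no figure to reproduce: the sample is one of convenience, with no alpha, power, effect size or SD stated.

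Inputs from the protocol:
- 50 patients, half per arm, so n = 25 per arm (no dropout assumed).
- 6MWT in a cited exercise trial (exercise group n = 8): 321 ± 36 m rising to 417 ± 33 m. Whether ± is an SD or a standard error is not stated.

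Assumed inputs:
- Two-sided 5% t-test and no true effect.
- Encouragement bias b = 10 or 20 m in favor of the active arm.
- SD of the change s = 35, 70 or 102 m. The lowest is close to the cited spread read as an SD. The highest reads ± 36 m as a standard error: 36 × √8 = 101.8 m. The value of 70 m lies between them.

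The cited spread is for distance at one time point. With equal spreads and within-patient correlation r, the SD of change is the single-time SD × √(2(1 − r)). The two are equal only at r = 0.5, and r is not given.

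Formulas: SE = s × √(2/25). The probability of a significant result favoring the active arm is P(T > 2.011), where T is noncentral t with 48 degrees of freedom and noncentrality b/SE. With b = 0 this is 2.5%.

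| s (m) | SE (m) | b = 10 m: b/SE | False benefit | b = 20 m: b/SE | False benefit |
|---|---|---|---|---|---|
| 35 | 9.90 | 1.01 | 16.6% | 2.02 | 50.8% |
| 70 | 19.80 | 0.51 | 7.1% | 1.01 | 16.6% |
| 102 | 28.85 | 0.35 | 5.3% | 0.69 | 10.0% |

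The range is about 5% to 51%.

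**The case against.** **A shared role is not a shared person.** A reader might infer that the same individual coaches the active arm and runs its walk test. The documents do not support that. The protocol uses the word investigator generically; anthropometrics, for example, may be done by a dietitian or a designated investigator. This objection stands, and the point is limited to what the plan leaves open.

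**The CRET staff are not shown to be independent.** A reader might also infer that non-coaching staff already run the other fitness test and could simply take over the walk test. The protocol mentions the laboratory's procedure, a medical monitor and test personnel, so the CRET appears to have its own staff. It does not say that they do no coaching, are unaware of allocation or are free for walk tests. This stands too, so using them has to be conditional.

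**The plan does mask elsewhere.** It would be wrong to say that only a secondary assay is protected. The CT reading for the other primary aim is de-identified and done off site, and controls cannot see their step counts. The gap concerns the effort-dependent fitness tests.

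**Encouragement may already be standardized.** The 6MWT section follows American Thoracic Society recommendations and then only summarizes them. That source is not available here, so a missing script is not shown. However, the protocol itself still does not say who tests or what the tester knows.

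**The size rests on assumptions.** No document supports a bias of 10-20 m, or any bias at all, and 51% pairs the largest assumed bias with the smallest SD. This stands: the figures show sensitivity and do not predict what will happen.

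**Conclusion.** The point holds as a gap in the plan. For a primary measure that depends on effort, the protocol neither blinds the tester nor separates the tester from the coach of the active arm. The exposure is at the week-12 and post-transplant tests; baseline tests precede randomization and are not affected.

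Under the assumptions set out above, a false benefit on the 6MWT would occur in about 5-51% of trials instead of 2.5%. Every value in the table is above the nominal rate, but each depends on a bias that is supposed rather than documented. The change is worth making because it is cheap beforehand and the problem is hard to repair once the tests are done.

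**What to change.** In the CRET and 6MWT sections, and in Follow Up where visits are described, state that:

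1. The week-12 and post-transplant 6MWT and CRET are run by existing staff who deliver no behavioral therapy and are not told the allocation. The personnel who run the CRET are one option, once their independence from coaching is confirmed.
2. Patients are asked before each of these tests not to disclose their arm.
3. The same standardized encouragement is used in both arms. First confirm whether the cited American Thoracic Society procedure already covers this; if it does, say so explicitly.

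Baseline tests need no blinding.

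**Cost.** If suitable existing staff are confirmed, no extra assessor is needed. The burden is scheduling: at baseline the CRET is on Day 1 and the 6MWT on Day 3 of the same week, so a similar follow-up schedule would need the testers on a second day. Blinding will be imperfect if patients talk, but separating tester from coach and standardizing encouragement still help when it fails.

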oxygen uptake and carbon dioxide outflow will be performed during the test, in order to determine VO_2 (oxygen consumption) and VCO_2 (carbon dioxide consumption) in real time. The $\text{VO}_{2\text{max}}$ will be identified as a clear plateau in the VO_2 curve. In cases where no plateau can be observed due to exhaustion, the $\text{VO}_{2\text{peak}}$ at the time of test termination will be used as an equivalent. The anaerobic threshold will be identified by means of the V-slope method on the VO_2 to VCO_2 plot (respiratory exchange ratio).(38) Thirty minutes after completion of the test, each patient will be clinically evaluated for clinical signs of HE according to standard criteria (Table 1 and Figure 2). This test will be repeated after completion of the study period (12 weeks), and 6 months after LT.

Ammonia and lactate thresholds (Week -1, Day 1)

In order to obtain frequent venous samples, an 18-20 Ga IV catheter with a saline lock will be placed in the forearm before the test. Ammonia levels will be determined on venous samples with an automated point-of-care device (PocketChem Ammonia Checker II, Arkray Inc., Kyoto, Japan), prior to the start of the test, and then repeated every 3 minutes until termination of test, with a final sample 20 minutes after termination of the test. This will allow identification of the ammonia threshold when results are plotted against % $\text{VO}_{2\text{max}}$. After a baseline determination of lactate, repeated samples will be obtained every 2 minutes, immediately after the test is finished, and 20 min after termination. This will allow correlating the anaerobic threshold obtained from the respiratory exchange ratio with the lactate threshold. For both the ammonia and lactate thresholds is it estimated that 6-7 blood draws will be performed per patient (4 mL per sample) corresponding to 24-28 mL in total. These two tests will be repeated after completion of the study period (12 weeks).

Six-minute walk test (6MWT) (Week -1, Day 3)

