The questionnaire Sickness Impact Profile (SIP) will be used to assess changes in the quality of life. Recent evidence suggests SIP to be superior to SF-36 in detecting health-related quality of life changes occurring in patients with ESLD. Metabolic profile will include determinations of fasting glucose, insulin (in subjects without diabetes mellitus), lipid profile (triglycerides, total-cholesterol, HDL-cholesterol, LDL-cholesterol), and HbA1c. Both SIP and the metabolic profile will be repeated after completion of the study period (12 weeks). The metabolic profile will be repeated 6 months after LT as well.

Randomization

Each participant will be randomly assigned to the active (physical activity + behavioral therapy + nutritional intervention) or control (nutritional intervention) group. The random allocation sequence will be generated using computer-generated random numbers. There will be no stratification in the randomization process, and allocation will be concealed.

Statistical analysis

Subjects sample has been defined by convenience, as there is no precedent for sample estimation. Descriptive statistics will include mean \pm SD and/or median (range), according to distribution of data. Shapiro-Wilk test will be used to assess normal distribution. Results on VCO₂ will be plotted against VO₂, whereas lactate, and ammonia will be plotted against VO_{2max}, for all patients as an aggregate. The lines determining the anaerobic, lactate, and ammonia thresholds will be calculated by linear regression. Continuous variables comparisons within groups will be done with paired t-test or Wilcoxon, whereas between groups will be done with t-test or Mann-Whitney. Categoric variables will be compared with chi-square or Fisher's exact test, as appropriate. Agreement between methods used to address body composition, bioelectrical impedance and DXA, will be investigated with Bland-Altman test.

Data collection and handling

Title: A physical activity program in end-stage liver disease
PI: [name]

Apart from the data generated by the study demographics and clinical information to properly classify the hepatic functional and cardiorespiratory status of each participant will be retrieved from the electronic medical record (EMR). Such information will include results from standard of care laboratories, imaging, and other special studies (EGD, pulmonary function tests, echocardiogram), to calculate MELD score, and Child-Turcotte-Pugh scores.

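### The statistical section pools the lactate and ammonia threshold plots across patients on a VO2max axis, while the aim and the planned tests need one threshold per patient and visit on % VO2max

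*Combined protocol and SAP*

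**What the plan says.** Specific Aims lists, as the first secondary aim, "The changes in the ammonia and anaerobic/lactate thresholds at the end of the study for each group". The stated expectation is a between-arm one: "It is expected to find increased ammonia and anaerobic/lactate thresholds in the active arm, when compared to the control arm".

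The Statistical analysis section plots VCO2 against VO2, and lactate and ammonia against VO2max, "for all patients as an aggregate. The lines determining the anaerobic, lactate, and ammonia thresholds will be calculated by linear regression". It then gives the tests: "Continuous variables comparisons within groups will be done with paired t-test or Wilcoxon, whereas between groups will be done with t-test or Mann-Whitney".

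Other sections treat thresholds as belonging to individual patients:

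- Physical Activity refers to thresholds "observed on each subject will help better determine the intensity of exercise each patient should be able to tolerate safely".
- The section on the cardiorespiratory stress test states: "The anaerobic threshold will be identified by means of the V-slope method".
- The section on ammonia and lactate thresholds samples ammonia at rest, at 3-minute intervals during exercise and 20 minutes into recovery. Lactate is sampled at rest, at 2-minute intervals, at the end of exercise and 20 minutes into recovery. On ammonia it says "This will allow identification of the ammonia threshold when results are plotted against" % VO2max. On lactate it says "This will allow correlating the anaerobic threshold obtained from the respiratory exchange ratio with the lactate threshold".
- The Introduction describes the ammonia threshold as a deflection point and cites Figure 1c, which is not shown.

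**The concern.** A t-test, Wilcoxon or Mann-Whitney test needs a value from each patient. The correlation of anaerobic with lactate threshold needs one pair per patient. A line fitted to pooled data supplies neither. The horizontal axis is also inconsistent: VO2max is a single number per test, so a within-test rise cannot be located on it, whereas the test description uses % VO2max.

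For the anaerobic threshold, V-slope fills the gap. For lactate and ammonia, the visible text gives the samples, a plot and a concept. It does not say how the point is found in one patient's test, or what is recorded if none appears. If the rule is settled only after week-12 tests have been read, the choice can follow the data. Tests stop when the patient is exhausted or the monitor ends them, so some may stop before a threshold is seen. Under the sponsor's own hypothesis of higher thresholds with training, that may happen more often in the active arm.

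**Working it through.** The sample is one of convenience, so the plan has no power figure to reproduce.

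**1. Values needed and values supplied.** Inputs: 50 patients, half per arm, tested at baseline and week 12.

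- Needed for lactate and ammonia: 50 × 2 visits × 2 markers = 200. For the anaerobic threshold: 50 × 2 = 100, covered by V-slope.
- Supplied by the literal rule: 1 per marker, 3 in all. Split by arm and visit (not stated): 3 × 2 × 2 = 12, with no between-patient variance within a cell.
- With per-patient values and no losses, a between-arm t-test has 25 + 25 − 2 = 48 degrees of freedom.

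**2. How many samples one test gives.** Test length is not stated; I assume 6 to 15 minutes. The planned 6-7 blood draws do not settle it. Counting the recovery sample, they match the combined schedule at 5-8 min, lactate alone at 7-10 min, or ammonia alone at 12-17 min.

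- Ammonia at 0, 3, 6, … min: 3 to 6 values before recovery.
- Lactate at 0, 2, 4, … min plus end of test: 4 to 9 values.
- A two-segment fit has 4 parameters (intercept, two slopes, break). Residual degrees of freedom are 3 − 4 = −1 to 6 − 4 = 2 for ammonia, and 4 − 4 = 0 to 9 − 4 = 5 for lactate.
- One sampling interval as a share of exercise time (not of % VO2max): ammonia 3/15 = 20% to 3/6 = 50%; lactate 2/15 = 13% to 2/6 = 33%.

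**3. Illustration: what dropping unreached tests would do.** The plan gives neither a rate nor a dropping rule, so every input is assumed: normal thresholds with SD 1, true difference 0.5 SD, and a common cap c with a share p of control tests above it. Then c = z(1 − p) and

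kept difference = [0.5 − φ(c − 0.5)/Φ(c − 0.5)] + φ(c)/Φ(c).

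At p = 0.05, c = 1.645: 0.5 − 0.237 + 0.109 = 0.372. The SDs of kept tests are 0.900 (control) and 0.820 (active), so the standardised difference is 0.372 / √[(0.900² + 0.820²)/2] = 0.43.

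| Control tests unreached | Active tests unreached | Raw difference kept (SD) | Standardised by SD of kept tests |
|---|---|---|---|
| 5% | 13% | 0.37 | 0.43 |
| 10% | 22% | 0.32 | 0.40 |
| 20% | 37% | 0.26 | 0.36 |

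**4. Baseline adjustment.** For 25 analysable patients per arm, two-sided 5% and 80% power, a two-sample t-test detects 0.809 SD. With baseline to week-12 correlation r (assumed), multiply by √[2(1 − r)] for a t-test on change and by √(1 − r²) for ANCOVA, ignoring the one degree of freedom lost.

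| r | t-test on change | ANCOVA |
|---|---|---|
| 0.5 | 0.809 × 1.000 = 0.81 | 0.809 × 0.866 = 0.70 |
| 0.7 | 0.809 × 0.775 = 0.63 | 0.809 × 0.714 = 0.58 |
| 0.8 | 0.809 × 0.632 = 0.51 | 0.809 × 0.600 = 0.49 |

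**The case against.** The strongest reply is that the plan intends individual thresholds and nearly says so. The phrase about aggregation closes the plotting sentence and need not govern the regression sentence. Serial samples are taken from every patient, and Physical Activity speaks of each subject's thresholds. Regression lines together with a deflection point suggest two intersecting lines, and Figure 1 may show this. VO2max in the Statistical analysis section may be shorthand for % VO2max. All of that stands, and it limits the point to specification.

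A reader might infer that the aim cannot be analysed, or that the regression conflicts with V-slope. The documents support neither. The patient-level data are collected, and V-slope uses the same VO2 and VCO2 plot that the regression sentence covers.

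A reader might also infer that a sparse schedule defeats any fit, or that unreached tests will be dropped. In a simulation with six points per patient (25 patients, assumed thresholds with mean 60 and SD 10 % VO2max), individual two-segment fits gave a mean near 60 and an SD near 11, so that count was usable; shorter tests give fewer points. A convention applied alike in every test shifts both arms and visits similarly, so much of the sampling-interval effect cancels in the comparison. No section says that unreached tests are dropped. The Introduction suggests that ammonia may rise early in these patients, which would make unreached ammonia thresholds less common.

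Finally, a t-test or Mann-Whitney test on patient-level values is valid under randomisation. Baseline adjustment is a matter of efficiency.

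What remains is that the only statistical text on thresholds describes a pooled derivation on an axis that differs from the test description, and no visible text says how a lactate or ammonia threshold is located in one test.

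**Conclusion.** The point holds as an inconsistency and a specification gap in one secondary aim. Read literally, the Statistical analysis section yields 3 (or 12) cohort values where its own tests, the between-arm aim and the anaerobic-lactate correlation need patient-level ones. It also departs from the % VO2max axis used elsewhere. The gap covers up to 200 lactate and ammonia values and leaves the anaerobic threshold untouched. It is judged on visible text only, since Figure 1 could not be read.

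The dropping figures are illustrative. They rest on assumed normal thresholds, a common cap and assumed rates, and on the standardised scale that a t-test uses the loss is smaller than on the raw scale. The ANCOVA figures assume 25 analysable patients per arm and the stated correlations. The change should be made, but it does not touch the primary aims.

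**What to change.** In the Statistical analysis section:

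1. Derive each threshold per patient and per visit. Keep V-slope for the anaerobic threshold. For lactate and ammonia, state one rule on the % VO2max axis, chosen and justified by the sponsor, that excludes the 20-minute recovery sample and is fixed before week-12 tests are read. A deflection-point fit keeps the protocol's construct; name a simpler rule for tests with too few samples to fit one.
2. Report tests with no threshold reached, by arm and visit, and keep them in the comparison, for example as the highest rank in the Mann-Whitney test that is already planned, applied to week-12 values.
3. Compare arms at week 12 by ANCOVA with the baseline threshold as covariate. ANCOVA needs a number for every test, so state in advance what is entered for unreached ones and whether this analysis or the rank analysis leads.
4. Keep the aggregate plot as a descriptive figure.

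The cost is plan wording and modest extra analysis, with no new measurement. Some tests will still have no identifiable threshold, and ranking them highest is an assumption that should be stated as such.
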